### **5.3.10 Week 10, Follow-up visit/End of Study**

During the last visit of the study, expected to occur 2 weeks following the final light treatment, the following assessments will be performed:

The patient will complete the VASitch form and the data transcribed into the eCRF.

Vitals taken (heart rate, respiratory rate, and sitting blood pressure).

Hematology panel drawn.

Clinical chemistry panel drawn.

5 mL of blood obtained and processed for serum hypericin levels.

CAILS scores for the 3 index lesions will be measured and recorded.

The mSWAT and PGA scores will be assessed and recorded.

A 12-lead ECG obtained including QT interval measurements.

Patients will be asked about any AEs experienced since the last light session and these will be recorded in the eCRF. Information on all unresolved, previously reported AEs will be obtained.

#### **5.4 Premature Discontinuation**

Patients have the right to withdraw from this trial at any time (as described in the informed consent document) without prejudice to further care. An investigator may withdraw a patient from the study at any time for any of the following reasons:

- The patient withdraws his/her consent or refuses follow-up evaluations.
- The patient is lost to follow-up and will not attend further study visits.
- The investigator determines that further participation would be detrimental to the patient's health or well-being.
- The patient fails to comply with the study requirements so as to cause harm to self or seriously interfere with the validity of the study results.
- The female patient becomes pregnant during the treatment period. In this case, treatment should be halted and the patient followed until the end of the pregnancy. If a child is born, the infant should be followed through at least 6 months of age.
  - At the discretion of the site investigator if he/she feels that it is in the best medical interest of the patient.

Patients withdrawn from the study will have as many of the trial assessments completed as the patient permits including blood tests and lesion evaluations.

Patients withdrawn from the study may be replaced up to a total of 8 subjects provided that both the PI and the Soligenix Medical Monitor agree that the reasons for withdrawal do not suggest a change in the risk assessment of the HyBryte therapy.

### **6 DESCRIPTION OF STUDY PROCEDURES**

Subjects will have the following procedures performed.

#### **6.1 Light Session**

The amount of visible light to be delivered will start at 5 J/cm^2 and be titrated up until either the patient experiences a mild (Erythema Grade 1) response to the light treatment 5-10 minutes post-treatment or a dose of 25 J/cm^2 is reached, whichever occurs first. The

duration of light treatment is dictated by the light treatment table listed below ([Table 4](#)). Depending on the distribution of the patient's lesions, more than one position for light treatments may be necessary.

**Table 4: Duration of Light Exposure Required for Given Light Doses**

Light Dose (J/cm  )	Duration (Min: Sec)
5	10:49
6	12:59
7	15:09
8	17:19
9	19:29
10	21:39
11	23:49
12	25:58
13	28:08
14	30:18
15	32:28
16	34:38
17	36:48
18	38:58
19	41:08
20	43:17
21	45:27
22	47:37
23	49:47
24	51:57
25	54:07

## 6.2 Electrocardiogram (ECG)

12-lead ECGs, including QT interval measurement, will be done at baseline (prior to drug application), Week 4, Session 2 (immediately prior to and 2 hours after the light session), Week 6, Session 2 (immediately prior to the light session), Week 8, Session 2 Light Session Visit (immediately prior to and 2 hours after the light session), and at the Week 10 Follow-up visit. ECG will be interpreted by site personnel trained in the evaluation of ECGs for any interval changes.

### 6.3 Hypericin Blood Levels

Blood samples for pharmacokinetic analysis will be collected at the following timepoints:

- Baseline, prior to drug application
- Week 4 Session 2, prior to light session
- Week 4 Session 2, 2 hours after completion of the light session
- Week 6 Session 2, prior to the light session
- Week 8 Session 2 Drug Application visit, prior to drug application
- Week 8 Session 2 Light Session visit, 2 hours after completion of the light session
- Week 10/End of Study follow-up visit

Blood samples will be collected with K2EDTA tubes and mixed (inverting top to bottom) at least 5 times after collection. Tubes will be placed on wet ice pending transfer to labeled 2 mL amber vials or tubes and then frozen (temperature  $\leq -60$  °C). The times that samples are collected and frozen must be noted.

Blood will be processed and shipped to the central laboratory as detailed in the “HPN-CTCL-02 Laboratory Manual For Pharmacokinetic Sample Collection”. Samples will be shipped on dry ice to:

### 6.4 Clinical Laboratory Tests

#### 6.4.1 Hematology Tests

The hematology panel will be performed on blood obtained at baseline, Week 8, Session 2 Light Session visit prior to the light session, and Week 10/End of Study. The panel will consist of the following tests:

Red blood cell count (RBC)

Hematocrit

Hemoglobin

Mean corpuscular volume (MCV)

Mean corpuscular hemoglobin (MCH)

Mean corpuscular hemoglobin concentration (MCHC)

Platelet count

White blood cell count (WBC)

Percent and absolute neutrophil count

Percent and absolute lymphocyte count

Percent and absolute monocyte count

Percent and absolute eosinophil count

Percent and absolute basophil count

#### **6.4.2 Clinical Chemistry Laboratory Tests**

The clinical chemistry panel will be performed on blood obtained at baseline, Week 8, Session 2 Light Session visit prior to the light session and during the Week 10/End of Study follow-up visit. The panel will consist of the following tests:

Serum sodium

Serum potassium

Serum chloride

Serum bicarbonate (CO2)

Alanine aminotransferase (ALT)

Aspartate aminotransferase (AST)

Total bilirubin

Total protein

Serum creatinine

Blood urea nitrogen (BUN)

Alkaline phosphatase

## 6.5 Vital Signs

Vital signs will be obtained by site personnel at baseline, Week 8, Session 2 Light Session visit prior to the light session and during the Week 10/End of Study follow-up visit. Vital signs obtained will consist of:

- Resting Blood Pressure
- Heart Rate
- Respiratory Rate

## 6.6 Quality of Life Assessments

The Skindex-29, a self-administered survey instrument to measure the effects of skin disease on patients' quality of life will be administered at baseline and at Week 8 Session 2 Light Session visit ([Appendix III](#)). Patients will complete the form on their own and site personnel will review and assure that the form is complete.

## 6.7 VAS Itch Assessment

The Visual Analog Score for Itch (VASitch) is a patient reported outcome measurement of the degree of itchiness that the patient has experienced over the preceding 24 hours and will be administered at baseline, each light treatment, and the Week 10/End of Study visit. Patients will be instructed to place a vertical mark on a 10 cm line with a 0 (none) at the right side and a 10 (the worst itch you can imagine) at the left indicating the amount of itch that they have experienced over the preceding day. The score will be recorded as the distance in centimeters (to 1 decimal place) between the 0 mark and the vertical line that the patient drew.

## 6.8 Composite Assessment of Index Lesions Severity (CAILS) Score

The CAILS score will be assessed for the prospectively identified representative lesions at baseline and at the Week 10/End of Study visit. CAILS score will be calculated by assessing the erythema ([Table 5](#)), scaling ([Table 6](#)), plaque elevation ([Table 7](#)) and involved surface area ([Table 8](#)) for each of the index lesions. Each of the assessments and the total score for each evaluated lesion will be recorded in the case report form (CRF). The total CAILS score will be calculated by adding the scores of all evaluated lesions together.

**Table 5: Erythema Subscore of the modified CAILS Score**

Score	Description
0	No evidence of erythema, possible brown hyperpigmentation
1	*
2	Mild: Light red lesion
3	*
4	Moderate: Red lesion
5	*
6	Severe: Very red lesion
7	*
8	Very severe: Extremely red lesion

\* Intermediate intervals 1, 3, 5, and 7 are to serve as mid-points between the defined grades 0, 2, 4, 6, and 8

**Table 6: Scaling Subscore of the modified CAILS Score**

Score	Description
0	No evidence of scaling on lesion
1	*
2	Mild: Mainly fine scales: lesion partially covered
3	*
4	Moderate: Somewhat coarser scales: lesion partially covered
5	*
6	Severe: Coarse, thick scales; virtually all of the lesion covered; rough surface
7	*
8	Very severe: Coarse, very thick scales; all of the lesion covered very rough surface

\* Intermediate intervals 1, 3, 5, and 7 are to serve as mid-points between the defined grades 0, 2, 4, 6, and 8

**Table 7: Plaque Elevation Subscore of the modified CAILS Score**

Score	Description
0	0 mm: No evidence of plaque above normal skin level
1	Mild elevation
2	Moderate elevation
3	Marked elevation

**Table 8: Surface Area Subscore of the modified CAIIS Score**

Longest diameter and the longest diameter perpendicular to this diameter of each index lesion will measured to the nearest millimeter. The lesion area will be the product of these two diameters	
Score	Area
0	0 cm 
1	>0 and ≤4 cm 
2	>4 and ≤10 cm 
3	>10 and ≤16 cm 
4	>16 and ≤25 cm 
5	>25 and ≤35 cm 
6	>35 and ≤45 cm 
7	>45 and ≤55 cm 
8	>55 and ≤70 cm 
9	>70 and ≤90 cm 
10	>90 and ≤110 cm 
11	>110 and ≤130 cm 
12	>130 and ≤155 cm 
13	>155 and ≤180 cm 
14	>180 and ≤210 cm 
15	>210 and ≤240 cm 
16	>240 and ≤270 cm 
17	>270 and ≤300 cm 
18	>300 cm 

## 6.9 The Physician Global Assessment (PGA)

The PGA represents the investigator's assessment of the overall extent of improvement or worsening of the patient's cutaneous disease compared with baseline as shown in [Table 9](#). This assessment is designed to consider ***all cutaneous lesions***, including both index and non-index lesions. PGA score will be assessed at Week 10/End of Study.

**Table 9: Physician's Global Assessment**

Grade	Description
0 completely clear	No evidence of disease; 100% improvement
1 almost clear	Very obvious improvement ( $\geq 90\%$ to $< 100\%$ ); only traces of disease remain
2 marked improvement	Significant improvement ( $\geq 50$ to $< 90\%$ clear); some evidence of disease remains
3 moderate improvement	Intermediate between marked and mild ( $\geq 25\%$ to $< 50\%$ )
4 slight improvement	$\geq 10\%$ to $< 25\%$ ; significant evidence of disease remains
5 no change	Disease has not changed significantly from baseline (10 to -25%)
6 condition worse	Disease is worse than baseline by $\geq 25\%$

## 6.10 Modified Severity Weighted Assessment Tool (mSWAT)

The mSWAT is designed to quantify the disease burden associated with CTCL and is based on an estimate of the percent total area of skin involved based on the BSA. The types of lesions are weighted by the lesion characteristic (patch, plaque, or tumor) as shown in [Table 10](#). The mSWAT score will be assessed at baseline and at Week 10/End of Study.

**Table 10: Modified Severity Weighted Assessment Tool (mSWAT)**

Body Region	% BSA  in Body	Assessment of Involvement in Patient's Skin		
		Region	Patch 	Plaque 
Head	7%			
Neck	2%			
Anterior trunk	13%			
Arms	8%			
Forearms	6%			
Hands	5%			
Posterior trunk	13%			
Buttocks	5%			
Thighs	19%			
Legs	14%			
Feet	7%			

Body Region	% BSA  in Body Region	Assessment of Involvement in Patient's Skin		
		Patch 	Plaque 	Tumor 
Groin	1%			
Weighting Factor		x1	x2	x4
Subtotal lesion BSA x weighting factor				

 BSA = body surface area

 Any size lesion without induration or significant elevation above the surrounding uninvolving skin; poikiloderma may be present.

 Any size lesion that is elevated or indurated; crusting, ulceration, or poikiloderma may be present.

 Any solid or nodular lesion >1 cm in diameter with evidence of deep infiltration in the skin and/or vertical growth.

## 6.11 Erythema Scoring

Approximately 5-10 minutes before and after the completion of light therapy, treated lesions will be graded for erythema with the worst, best, and “average” scores recorded. The reaction will be graded using the definitions in [Table 11](#).

**Table 11: Skin Phototoxicity Grading**

Toxicity Grade: Erythema and/or Edema	Severity
Grade 0	No apparent reaction
Grade I	Mild
Grade II	Moderate
Grade III	Severe with edema
Grade IV	Life-threatening with vesication

## 7 STUDY DRUG MANAGEMENT

### 7.1 Description

HyBryte is synthetic hypericin formulated as a 0.25% hypericin (2.5 mg/gram) ointment. The ointment is lavender/purple.

#### 7.1.1 *Study Drug Packaging and Labeling*

HyBryte will be supplied in plastic screw-top jars containing 25 grams of 0.25% hypericin (2.5 mg/gram). Jars will be labeled with the study number (HPN-CTCL-02), HyBryte™ (0.25% Hypericin) and the warning "Caution: New Drug-Limited by U.S. Federal Law to Investigational Use."

### 7.3 Administration

After adequate patient training, patients will apply HyBryte ointment to all accessible CTCL lesions, applied to cover a thin layer of drug the entire surface of each lesion. However, application to uninvolved skin should be as limited as possible. The amount of ointment used for each application will be dependent upon the amount of lesion surface area. Personnel applying the drug should wear disposable gloves and wash their hands after applying the study ointment. If the medicine gets on healthy skin, it should be washed-off with soap and water. Patients will bring their drug jars to the clinic at each light treatment and site personnel will weigh the jars to estimate the amount of drug applied.

### 7.4 Study Drug Accountability

The PI must ensure that all drug supplies are kept under lock and key with access limited to those authorized by the investigator until distributed to patients. The PI must maintain accurate records of the receipt of all study medication shipped by the Sponsor, including date received, lot number, expiration/re-test date, amount received and disposition of all study medication. Current dispensing records will be maintained and include date and amount of medication dispensed, initials of subjects receiving the medication, and any amount of medication not used or returned (or lost) by the subject. All remaining medication not required by regulation to be held by the clinical facility, must be destroyed following all appropriate regulatory guidelines or returned to the Sponsor

immediately after the study is completed. Any lost, spilled or missing drug must be documented.

Patients will be instructed to store the drug in their refrigerator.

## **7.5 Study Drug Handling and Disposal**

Disposable gloves should be used when applying the drug to skin lesions and after applying the ointment, hands and any areas receiving other unintended ointment should be washed with soap and water.

## **7.6 Prohibited Concomitant Medication**

Prior medications, going back 3 weeks from the screening date (systemic and topical), will be collected at the screening visit. Concomitant medications (systemic and topical) will be collected at each clinic visit.

The following drugs are **not allowed within 2 weeks** of enrollment or during the study:

Topical steroids (including 1% hydrocortisone cream or ointment)

Other topicals (nitrogen mustard, carmustine/BCNU, retinoids, imiquimod)

The following drugs are **not allowed within 3 weeks** of enrollment or during the study:

Systemic steroids

Psoralen UVA radiation therapy (PUVA)

Narrow band-UVB

Other systemic therapies for CTCL

The following drugs are **not allowed within 30 days** of enrollment or during the study:

Investigational drugs

Drugs of abuse

The following drugs are **not allowed within 3 months** of enrollment or during the study:

Radiation therapy (localized or total skin)

Patients taking medication to cause photosensitization must be discontinued for at least 2 weeks prior to initiating HyBryte or have been on a stable dose of such drugs without any evidence of photosensitivity for a period of no less than 4 weeks. A list of the most common photosensitizing agents are as follows:

- Antibiotics: tetracyclines (doxycycline, tetracycline), fluoroquinolones (ciprofloxacin, ofloxacin levofloxacin), sulfonamides
- Nonsteroidal anti-inflammatories: ibuprofen and ketoprofen
- Diuretics: furosemide and hydrochlorothiazide
- Retinoids: isotretinoin and acitretin
- Hypoglycemics: sulfonylureas (glipizide, glyburide)
- PDT pro-photosensitizers: 5-aminolevulinic acid, methyl-5-aminolevulinic acid, verteporfin, Photofrin
- Neuroleptic drugs: phenothiazines (chlorpromazine, fluphenazine, perazine, perphenazine, thioridazine), thioxanthenes (chlorprothixene, thiothixene)
- Sunscreens: para-aminobenzoic acid (PABA), cinnamates, benzophenones, salicylates
- Fragrances: musk ambrette, 6-methylcoumarin
- Others: 5-FU, amiodarone

## 7.7 Compliance

Containers will be weighed before each light session. Any study drug discarded (eg, wiped off healthy skin, dropped or otherwise discarded) will be recorded.

## 8 ADVERSE EVENTS

Timely, accurate and complete reporting and analysis of safety information from trials is crucial for the protection of subjects, investigators and the Sponsor, and is mandated by regulatory agencies worldwide. Soligenix has established standard operating procedures (SOPs) in conformity with regulatory requirements to ensure appropriate reporting of safety information. All trials that are the responsibility of Soligenix must be conducted in accordance with the procedures as provided below.

### 8.1 Definitions

#### 8.1.1 **Adverse Event (AE)**

Any noxious or unintended event that occurs in association with the use of an investigational agent in humans, ***whether considered related to the investigational agent or not.*** This definition encompasses symptoms or signs reported by the subject or detected by the investigator or other competent observer, as well as medically important deviations from normality in the results of ancillary investigations. If present at time of first dose of study drug, such AEs must be recorded as part of the medical history.

#### 8.1.2 **Treatment-Emergent AE**

An AE that is new in onset or aggravated in severity or frequency following entry into the study. In addition, any pathological finding on physical examination or diagnostic procedure that is new in occurrence or exacerbated in comparison with the subject's status at study entry is considered a treatment-emergent AE if it requires any medical or surgical intervention whatsoever (including, but not limited to, additional diagnostic procedures or alteration of prescribed therapy).

#### 8.1.3 **Potentially Serious AE**

Any AE that is sufficiently severe or alarming as to require any form of significant medical intervention. Note: Important medical events that may not result in death, be life threatening, or require hospitalization may be considered an SAE when, based upon appropriate medical judgment, they may jeopardize the subject and require medical or surgical intervention to prevent one of the outcomes listed in the SAE definition.

### 8.2 Relationship to Study Drug

The relationship of an AE to the assigned study drug is assessed using the following definitions:

- **Not Related:** The drug experience is clearly related to other factors such as the patient's/subject's clinical state, therapeutic interventions or concomitant drugs.
- **Possibly Related:** The drug experience follows a reasonable sequence from the time of drug administration and/or follows a known response pattern to the

study drug, but could have been produced by other factors such as the patient's/subject's clinical state, therapeutic interventions or concomitant drugs.

- **Related:** The drug experience follows a reasonable temporal sequence from the time of drug administration and follows a known response pattern to the study drug, and cannot be reasonably explained by other factors such as the patient's/subject's clinical state, therapeutic interventions or concomitant drugs.

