### 2.2 Secondary

Assess the safety of HyBryte photodynamic therapy.

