### 8.4 Recording Adverse Events

All AEs, whether judged to be related or not to the study drug, should be recorded in both the medical record and the CRF. The start and resolution dates, the judgment of the severity of the AE, the judgment of the relationship of the AE to the study drug, the action taken for subsequent dose of study drug, and the outcome should be noted.

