### 7.1. Adverse Events

Summary tables will be provided for all treatment-emergent adverse events (TEAEs). Treatment-emergent AEs are defined as events whose onsets occur, or severity worsens on or after the date of first dose of study drug. All TEAEs will be included in summaries.

An overview table will contain the number and percentage of patients with any TEAEs, with study drug related TEAEs, serious adverse events (SAEs), with AEs causing death, with related AEs causing death, with related SAEs, with AEs causing study drug discontinuation, and with AEs causing discontinuation from the study.

The TEAE summary tables will include counts of patients. Therefore, if a patient experiences more than one episode of a particular TEAE, the patient will be counted only once for that event. If a patient has more than one AE that is coded to the same preferred term, the patient will be counted only once for that preferred term. Similarly, if a patient has more than one TEAE within a SOC, the patient will be counted only once in that SOC.

All AEs are to be reported from the time of first administration of study drug until study completion or discontinuation. The severity of all AEs is recorded as mild, moderate, or severe. If severity is missing for TEAE, it will be set to severe. If severity is missing for AE at pre-treatment, the severity will be set to mild: if severity change is not reported during the study, then severity of mild is retained for analysis. A treatment-related AE is defined as an AE with relationship to study drug recorded as related or missing in the CRF. All AEs will be coded using the MedDRA (Version 10.1).

The maximum severity of AE is defined as the AE with the worst severity experienced overall during the study, within a SOC, or within a preferred term.

The following TEAE summaries will be presented:

- Frequency of TEAEs by preferred term, sorted by decreasing overall total
- Frequency of TEAEs related to study drug, by SOC and preferred term
- Frequency of TEAEs related to study drug by preferred term, sorted by decreasing overall total
- Frequency of TEAEs by maximum severity, SOC, and preferred term
- Frequency of AEs causing discontinuation from the study drug and study by SOC and preferred term
- Frequency of SAEs by SOC and preferred term
- Frequency of TEAEs with seriousness of fatal by SOC and preferred term.

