Listings will be presented to show SAEs, AEs that resulted in early discontinuation from the study or study drug, and AEs with seriousness of fatal. A listing of all reported AEs will also be presented. For each adverse event the following will be specified: the treatment group, MedDRA system organ class, preferred term and adverse event description from the CRF, onset and resolution dates and their respective study days, duration, time of onset, severity, seriousness, AE or current condition number associated with the AE, and relationships to study procedure, the study drug and concomitant medication. The listing will display the outcomes as reported by the investigator.

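### Adverse event causality is asked only about the study drug, with the study light session not excluded from competing causes, so light-caused and drug-plus-light events can drop out of the related-event tables of a drug-plus-light therapy

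*Protocol*

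**What the plan says.** Protocol 4.1 and SAP 3 define a treatment as a drug application followed 18 to 24 hours later by a light session. The secondary objective in Protocol 2.2 is "Assess the safety of HyBryte photodynamic therapy", and SAP 2.2 repeats it.

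Protocol 8.2 opens the causality scale with "The relationship of an AE to the assigned study drug is assessed using the following definitions". It has three grades:

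- Not Related: "The drug experience is clearly related to other factors such as the patient's/subject's clinical state, therapeutic interventions or concomitant drugs".
- Possibly Related: the event fits the timing or the known pattern of the drug, "but could have been produced by other factors such as the patient's/subject's clinical state, therapeutic interventions or concomitant drugs".
- Related: the event fits both timing and pattern and "cannot be reasonably explained by other factors such as the patient's/subject's clinical state, therapeutic interventions or concomitant drugs".

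Protocol 8.4 asks sites to note "the judgment of the relationship of the AE to the study drug, the action taken for subsequent dose of study drug", and asks for no causality judgment against the light, the device or a procedure.

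SAP 7.1 then sets the counting rule: "A treatment-related AE is defined as an AE with relationship to study drug recorded as related or missing in the CRF". The related rows of the overview table and both related-TEAE frequency tables rest on it. In the same section, the listing of all adverse events is to show "relationships to study procedure, the study drug and concomitant medication".

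**The concern.** The question put to the investigator is narrower than the objective. The objective is about a two-part therapy and the scale is about one part. The other part is itself a therapeutic intervention in ordinary language, and nothing in Protocol 8.2 says it is not meant.

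The ambiguity falls on the toxicity that matters most. Protocol 1.2 states that phototoxicity was the only adverse event consistently reported with systemic hypericin, and phototoxicity needs drug and light together. For such a reaction, the answer to whether another intervention could explain it turns on whether the grader thinks of the light as part of the treatment or as something apart from it.

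At stake is what the related-event tables mean. A reader will take them as the events attributed to the therapy under study, whereas under the written rule they may hold only the events attributed to the ointment with confidence.

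**Working it through.** The plan gives no figure to reproduce, because SAP 5.1 calls the sample size arbitrary. The check is mainly a reading of Protocol 8.2 and 8.4 against SAP 7.1 and 8.2.

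**Step 1: follow each kind of event through the rules.**

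| Event | Grade the Protocol 8.2 wording allows | Treatment-related under SAP 7.1? |
|---|---|---|
| Effect of light or device alone (for example heat or long exposure), light read as an outside intervention | Not Related, if the cause is clear | No |
| Drug-plus-light reaction, light read as an outside intervention | Possibly Related, because another intervention could have produced it | No |
| Drug-plus-light reaction, light read as part of the study treatment | Related, if nothing else explains it | Yes |
| Grade left blank | Imputed as Related (SAP 8.2) | Yes |

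Two of the four routes lead out of the related-event tables. The imputation in SAP 8.2 helps only when the field is empty and does nothing for an event that was actively graded. Reading the light as part of the treatment does not settle the first row either: the question is still about the drug, so an effect of light alone has no clear grade.

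**Step 2: what the other outputs keep.** SAP 7.1 puts all TEAEs into summaries whatever their causality, by preferred term and by maximum severity, and tabulates SAEs, fatal events and discontinuations. All adverse events are listed. None of these tables shows attribution to the therapy.

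Protocol 10.2 adds two outputs:

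- Adverse events within 48 hours of ointment application, regardless of grade. The cover after the light session is 48 h minus the application-to-light interval minus the light duration. The interval is 18 to 24 h (Protocol 4.1) and the duration 10:49 at 5 J/cm² to 54:07 at 25 J/cm² (Protocol Table 4), assuming one light position.
  - Shortest: 48 h − 24 h − 54:07 ≈ 23.1 h
  - Longest: 48 h − 18 h − 10:49 ≈ 29.8 h

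  Early reactions are therefore caught and later ones are not.
- Serious or related events within 14 days of the last application. A non-serious event stays in this output only if it is related.

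Erythema is scored before and after each light session (Protocol 6.11, SAP 4.4.10), independently of causality, but SAP sections 6 and 7 plan no summary of those scores.

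**Step 3: weight of one patient.** Take one patient whose only related event is graded out of the related set. The related-TEAE rate then moves by 1/N:

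- N = 6 (Protocol 5.1): 1/6 = 16.7 percentage points
- N = 8 (maximum with replacement, Protocol 5.4): 1/8 = 12.5 percentage points

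**Step 4: protocol against SAP listing.** The SAP listing names a relationship to study procedure. Protocol 8.2 defines no such judgment and 8.4 does not ask for it.

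**The case against.** The best defence is that *therapeutic interventions* is undefined and stands next to clinical state and concomitant drugs, which suggests causes outside the study treatment. The documents treat light as part of that treatment: it activates the drug, and a treatment consists of both steps. Not Related also requires the event to be clearly due to something else. A post-light skin reaction fits the drug's known pattern and would more naturally be Possibly Related. This stands. A reader might infer that light-caused events are Not Related by definition, but the text only permits that grade, and mainly for effects of light or device alone.

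The defence does not close the gap, because Possibly Related is also outside the SAP 7.1 rule. The more natural grade for a phototoxic reaction still leaves the related-event tables.

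It is also fair to say that no event is lost. Every adverse event is recorded and listed, and with about 6 patients each case can be read individually. That stands too: the defect concerns the related subset only.

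Finally, safety is a secondary objective in an exploratory, uncontrolled study, and no test depends on the related rate. That limits the consequence without making the rule match the objective.

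**Conclusion.** The point holds in a limited form. The protocol's causality scale is drug-only and does not exclude the study light from the competing causes, and the SAP counting rule omits Possibly Related. Followed as written, light-caused events and drug-plus-light reactions can both be absent from the related-event tables of a study whose safety objective is the combined therapy. The mismatch over relationship to study procedure exists however the competing-cause wording is read.

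The conclusion rests on one inference, that a grader may count the study light as a therapeutic intervention. Nothing in the text rules this out or requires it.

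Three stronger readings go too far:

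- A reader might infer that the related rate will be biased low. The documents do not show how often events would be graded this way, and imputing missing causality as Related pushes upward. The 16.7 points (12.5 at the maximum of 8) is the weight of one reclassified patient and not an estimate of bias.
- A reader might infer that the procedure column of the listing will be empty. The CRF is not among the documents, and Protocol 8.4 does not claim to be its full specification, so only a mismatch between protocol and SAP can be shown.
- A reader might infer that results will differ by site. One site is named and a second is undecided, so this is speculation.

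The point is worth correcting because the change is small, but it does not touch the primary ECG and hypericin outcomes.

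**What to change.** - Protocol 8.2: state that the study light session is not one of the other factors in any of the three grades.
- Protocol 8.2 and 8.4: for each adverse event, collect one causality judgment for the study drug and one for the light session or procedure.
- SAP 7.1: define treatment-related as Related, Possibly Related or missing with respect to the drug, the light session or their combination. Use this definition for the related rows of the overview and for the related-TEAE tables, and show both attributions in the listing that already names study procedure.

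The cost is one extra CRF field per adverse event plus the wording. Counting Possibly Related for the drug needs no new data, since the protocol already has that grade. The downside is that the reported related-event rate may be slightly higher.
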